#### **Treatment of subjects**

All study subjects will be assessed by an anesthesiologist in the Preoperative Assessment Clinic (PAC) prior to their scheduled procedure date. At this time, subjects will undergo a comprehensive medical assessment, including a review of their current prescription medications. At the discretion of the reviewing

anesthesiologist, subjects will be counselled regarding which medications may be safely continued or held prior to their procedure.

All subjects will receive standard anesthetic, analgesic, amnestic, and anxiolytic medications under the care of a qualified anesthesiologist. Vasopressors will be used when appropriate as part of standard practice in the operating room. The choice of anesthetic technique will be at the discretion of the treating anesthesiologist, however the anesthetic adjuncts of dexmedetomidine, lidocaine, and ketamine will not be permitted due to significant potential for confounding due to independent effect on postoperative pain.

All patients will be premedicated with acetaminophen 975 mg on the day of their scheduled procedure in the Same Day Surgery (SDS) unit prior to arriving in the operating room. Once in the operating room, standard monitors including noninvasive blood pressure, electrocardiography, pulse oximetry, and capnography will be applied as per Canadian Anesthesiologists' Society (CAS) guidelines. Neither group will receive systemic dexamethasone for PONV prophylaxis; alternative PONV prophylaxis may include ondansetron or haloperidol, to be given at the discretion of the treating anesthesiologist.

Both groups will receive surgeon-placed, laparoscopically visualized transversus abdominus plane (TAP) block at the end of the surgical procedure prior to emergence from anesthesia as an analgesic adjunct using 1mL/kg of 0.25% bupivacaine with epinephrine 1:200,000 divided in four aliquots to be placed at two locations per side along the anterior axillary line between the costal margin and the iliac crest. The intervention group will have dexamethasone 16mg combined with the bupivacaine / epinephrine, with 4mg to be injected at each TAP site, for a total of 8mg dexamethasone per side. The study drug will be provided from wardstock available in the operating room, and will be prepared by nursing staff as per standard perioperative nursing practice. The control group will have TAP blocks with the same dose of bupivacaine without dexamethasone. The bupivacaine / lidocaine solution will be sourced from the hospital pharmacy, and is purchased from Sandoz Canada

Currently, the colorectal surgeons based at Royal University Hospital are experienced with performance of TAP blocks and have been performing them for several years. If there is interest from other general surgeons in participating in the trial, in-person training will be provided to that surgeon by one of the experience surgeons to ensure standardization of the technique.

Following surgery, patients will be extubated fully awake in the operating room and transferred to the PACU. In PACU, both groups will have access to nurse-administered multimodal analgesia including rescue hydromorphone for postoperative pain relief. Standard antiemetics will be available as well. Upon discharge from PACU, hydromorphone-based patient-controlled analgesia (PCA) will be initiated and continued for a minimum of 48 hours postoperatively. Morphine-based PCA can be substituted if there is a contraindication to hydromorphone. Both groups will receive acetaminophen 975mg PO Q6H scheduled for 48 hours then PRN.

Surgical ward nurses will be not informed that the patient is involved in the study, as participation is not relevant to postoperative care, which will be administered as per usual. The study institution maintains a standardized colorectal-surgery postoperative pathway directing advancement of diet, intravenous maintenance fluids, deep-vein thrombosis prophylaxis, and urinary catheter management.

#### **Assessment of efficacy**

The primary efficacy outcome of this study will be total opioid consumption, in hydromorphone equivalents, at 24 and 48 hours postoperatively. Secondary outcomes will be length of stay in the post-anesthetic care unit (PACU), length of stay in hospital, and total opioids administered in the PACU.

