### **Trial Objectives and Purpose**

The objective of this trial is to investigate the effect of adjuvant dexamethasone in combination with bupivacaine to increase the depth and duration of sensory block in laparoscopically placed transversus-abdominis plane (TAP) blocks. The primary outcome will be total opioid consumption, in hydromorphone equivalents, in the first 48 hours after surgery. Secondary outcomes will be length of stay in the post-anesthetic care unit (PACU) and length of stay in hospital. The results of this study will serve as a proof-of-concept and will guide future research exploring adjuvant dexamethasone use in TAP blocks, specifically optimal dosing and ultimately a head-to-head comparison with systemic dexamethasone.

The results of this study will be of benefit to patients presenting for colorectal surgery, and more likely any type of abdominal surgery. Further research and refinement of regional anesthesia protocols adds to the armamentarium of anesthetic modalities available to anesthesiologists and surgeons and may offer a strategy for improved patient care.

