#### **Trial Design**

This study will be carried out as a prospective, randomized, single-blinded clinical trial.

The intervention group will receive intraoperative laparoscopically assisted, surgeon-placed TAP blocks using 1mL/kg of 0.25% bupivacaine with epinephrine 1:200,000 combined with 16mg dexamethasone divided into 4 aliquots to be placed at two locations per side along the anterior axillary line between the

costal margin and the iliac crest. The control group will have TAP blocks with the same dose of bupivacaine without dexamethasone. The blocks will be performed at the conclusion of surgery. Postoperatively, all patients will be provided with patient-controlled analgesia (PCA) with institutional standardized orders.

Intravenous dexamethasone will not be given for prevention of postoperative nausea and vomiting (PONV); prophylaxis of postoperative nausea and vomiting will be at the discretion of the anesthesiologist, but can include any of ondansetron, haloperidol, or dimenhydrinate. If PONV occurs and is refractory to non-corticosteroid treatment, dexamethasone may be given for treatment but would result in exclusion from the trial. General anesthetic technique will be at the discretion of the anesthesiologist, but the following adjunct anesthetic drugs will not be permitted, due to independent effects on postoperative pain: dexmedetomidine, lidocaine, and ketamine. These adjuncts are occasionally used in anesthetic protocols, but their exclusion will not affect the quality of the anesthetic provided, and their use is not considered standard of care. All patients will be provided with a standardized hydromorphone-based patient-controlled analgesia (PCA) for a minimum of 48 hours postoperatively.

The primary outcome will be total opioid consumption, in hydromorphone equivalents, in the first 48 hours after surgery. Secondary outcomes will be length of stay in the post-anesthetic care unit (PACU), length of stay in hospital, and total opioids administered in the PACU.

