A computer-generated random number table will be used to randomize patients to receive either bupivacaine alone (n=60) or bupivacaine plus dexamethasone (n=60). Allocation will be performed in a 1:1 ratio. Group allocation will be concealed via a centralized third-party research assistant. Group allocation will be blinded to study participants, study investigators, post-anesthetic care unit (PACU) nursing staff, and surgical ward nursing staff. The attending surgeon and attending anesthesiologist on the day of surgery will not be blinded to the intervention, however, they will be asked to conceal the anesthetic modality from the PACU staff and ward nurses. The intervention will be charted in the Operating Room record, but not on the anesthetic record. PACU nurses commonly review the anesthetic record, whereby they would discover the intervention.

A blinded, centralized, third-party research assistant or study investigators will carry out data collection. Postoperative opioid consumption will be quantified through chart review as well as assessment of patient-controlled analgesia (PCA) usage at 24 and 48 hours following the operation. Recording the doses of opioids administered in the medication administration record (MAR) is standard practice by PACU nursing staff at the study institution. PCA pumps automatically document cumulative opioids administered and can easily be checked at the bedside, as well as being recorded in the MAR. Length of stay in hospital is readily available from the chart.

Followup for primary and secondary outcomes will be limited to 48 hours postoperatively, and assessment of infiltration sites for complications will be performed at 6 weeks postoperatively.

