#### Selection and withdrawal of subjects

We intend to enroll a sample size of 120 patients based on an alpha set at 0.05, power set at 0.08, and the effect size set at 0.8.

Inclusion criteria are: age > 18, ASA class I-III patients scheduled for elective or urgent inpatient laparoscopic/laparoscopic assisted colorectal surgery.

Exclusion criteria are: emergency surgery, open surgery, contraindications to laparoscopic surgery (ie. adhesions, inability to tolerate pneumoperitoneum), ASA class  $\geq 4$ , age < 18, pregnant or breastfeeding women, significant cardiorespiratory/hepatic/renal disease, allergy to any study drugs, inability to consent, inability to respond to pain assessments, inability to use the patient-controlled analgesia device (PCA), preoperative chronic opioid use.

Potential participants will be identified by their attending surgeon during their initial clinic surgical consultation. This typically occurs several weeks in advance of their scheduled surgical procedure. Information detailing the study, as well as contact information of the research team will be made available to patients at this time should they have any questions. After having had a chance to review the study information provided to them by their surgeon, prospective patients will be assessed by study staff (attending surgeon or designate such as a general surgery resident) and asked to sign a consent if they agree to participate and meet the inclusion criteria. The consent will be taken on the day of surgery.

Participants who are unable to personally provide informed consent will be excluded from the study. No third party will be allowed to consent on the participants behalf. Capacity will be assessed by the study staff or designate obtaining consent. All patients participating must be assessed to determine that they fully understand the protocol, risks, and benefits of participating in the study.

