#### **Statistics**

Primary Outcome:

Total opioid consumption at 24 and 48 hours will be gathered from the PCA record and Medication Administration Record (MAR). Intention to treat analysis will be performed. Parametric data will be analyzed with the students t-test for statistical significance.

Secondary Outcome: Opioid consumption in the PACU will be reported in hydromorphone equivalents and compared with chi square test. Length of stay in PACU and length of stay in hospital will be reported as a mean +/- standard deviation (SD), along with confidence intervals and compared with chi square test.

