#### **Interim Analysis**

Interim analysis for primary and secondary outcomes, as well as safety parameters, will be performed upon completion of 50% of the total recruitment. If statistically significant superiority of either arm is identified, the trial will be terminated.

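### The Protocol contradicts itself on whether 24-hour opioid consumption belongs to the primary outcome; the 48-hour total is primary throughout

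*Protocol*

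**What the plan says.** The Protocol defines or lists the primary outcome in four sections.

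- **Trial Objectives and Purpose**: "The primary outcome will be total opioid consumption, in hydromorphone equivalents, in the first 48 hours after surgery". This is one cumulative quantity.
- **Trial Design**: the same sentence. Later in that section, data collection includes "assessment of patient-controlled analgesia (PCA) usage at 24 and 48 hours following the operation".
- **Assessment of efficacy**: "The primary efficacy outcome of this study will be total opioid consumption, in hydromorphone equivalents, at 24 and 48 hours postoperatively". These are two quantities.
- **Statistics**, under its primary-outcome label: "Total opioid consumption at 24 and 48 hours will be gathered from the PCA record and Medication Administration Record (MAR"). Student's t-test is named for parametric data.

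The 24-hour total is not among the secondary outcomes in any of these sections. Selection and withdrawal of subjects gives one set of design figures, "alpha set at 0.05, power set at 0.08, and the effect size set at 0.8", with no time point attached. Interim Analysis states: "Interim analysis for primary and secondary outcomes, as well as safety parameters, will be performed upon completion of 50% of the total recruitment". There and in Stopping Criteria, superiority of either arm ends the trial, and neither section says on which outcome or at which time.

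**The concern.** Two sections make the 48-hour total the only primary outcome, and the section on efficacy adds the 24-hour total to it. Because no secondary list includes the 24-hour total, the text never gives it a lesser role that would settle the matter.

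If one time point is significant and the other is not, the Protocol supports two answers to whether the primary outcome was met, and the choice could be made with the results in view. The ambiguity also reaches the interim look, where a significant difference ends the trial and the deciding time point is not named.

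**Working it through.** **1. The texts side by side.**

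| Section | 0–48 h total | 24 h total |
|---|---|---|
| Trial Objectives and Purpose | primary | not mentioned |
| Trial Design, outcome statement | primary | not mentioned |
| Trial Design, data collection | reading time | reading time |
| Assessment of efficacy | primary | primary |
| Statistics | under the primary label | under the primary label, perhaps only as a reading time |
| Any secondary list | absent | absent |

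The 48-hour column is consistent. The 24-hour column is not, and the sentence in Assessment of efficacy is what makes it so.

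**2. Inputs for the size.** From the Protocol: alpha 0.05, 60 per arm, effect size 0.8. Assumed: two-sided tests (sidedness is not given), 0.8 as a standardised mean difference, and the correlation r between the 24-hour and 48-hour totals, for which the Protocol gives no value. The interim look is left out.

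**3. Type I error at one final analysis.** The two test statistics are taken as bivariate normal with correlation r, each tested at 0.05.

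- 48 hours alone: 0.05, the Protocol's own figure.
- At least one significant = 1 − P(|Z24| ≤ 1.96 and |Z48| ≤ 1.96).
- Both significant = 0.05 + 0.05 − P(at least one). At r = 0.9: 0.10 − 0.0704 = 0.0296.
- Exactly one = P(at least one) − P(both).

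| r | at least one | both | exactly one |
|---|---|---|---|
| 0.95 | 0.0646 | 0.0354 | 0.0291 |
| 0.90 | 0.0704 | 0.0296 | 0.0407 |
| 0.80 | 0.0781 | 0.0219 | 0.0561 |
| 0.70 | 0.0835 | 0.0165 | 0.0669 |

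(The last digit can differ by rounding.)

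**4. Which r is plausible.** The 0–24 hour total is part of the 0–48 hour total. With equal daily SDs and day-to-day correlation rho, r = sqrt((1 + rho)/2). So rho = 0 gives 0.71, 0.28 gives 0.80, 0.62 gives 0.90 and 0.80 gives 0.95. The range 0.8 to 0.95 is a judgement. With a day-2 SD of 1.5 times day 1 and rho = 0.3, r = 1.45/sqrt(4.15) = 0.71, so lower values cannot be ruled out.

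**5. How often the two tests disagree when there is an effect.** Simulated t-tests, 60 per arm, 200,000 trials per cell, the same standardised effect at both times:

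| Effect | r = 0.95 | r = 0.90 | r = 0.70 |
|---|---|---|---|
| 0.8 | 0.0056 | 0.0079 | 0.0135 |
| 0.5 (assumed) | 0.0769 | 0.1083 | 0.1879 |

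Disagreement is rare at 0.8 because power there is 0.991 at 60 per arm. At 0.5 power is 0.775, and the gap opens.

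**The case against.** The strongest reply is that 24 hours is only a reading time. Trial Design gives 24 and 48 hours as the times at which the PCA is checked, Statistics speaks of gathering totals at those times, and two sections give an identical single-outcome definition. On that view one loosely worded sentence stands against two explicit ones. This holds for Statistics. It does not rescue Assessment of efficacy, which names the outcome itself and says nothing about collection. If the reply describes the intent, correcting that sentence is what is needed.

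A second reply is that hierarchy and multiplicity rules belong in a SAP, which is not at hand. That is fair, and the absence of such a rule is not the point. The point is that the Protocol states its primary outcome in two ways that differ over 24 hours, and a SAP would have to depart from one of them.

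A third is that the effect is small. At the Protocol's own effect size, if it holds at both times, the tests almost never disagree, and the larger rates need an assumed effect of 0.5. This stands and limits the weight of the point.

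A reader might go further and infer that significance at either time suffices, so that type I error is inflated by design, or that both are required, so that the test is conservative (about 3.5% to 2.2% over r = 0.95 to 0.8). The documents support neither: the efficacy sentence joins the two times and states no success rule.

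**Conclusion.** The contradiction is real but narrow. It would be too strong to say that the Protocol has two incompatible primary outcomes, because the 48-hour total is primary in every statement; only the place of the 24-hour total conflicts.

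What this leaves open is a choice of time point after the data are seen. Such a choice would raise type I error from 5.0% to about 6.5% to 7.8% at r = 0.95 to 0.8. No section permits that choice; the text merely fails to exclude it. All these figures rest on the assumed r, two-sided tests and a single final analysis.

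The change should be made because it is nearly free and removes the choice before any unblinded look. The unadjusted interim threshold, the sample-size figures and the absence of PACU opioid use from the secondary list in Trial Objectives and Purpose are separate issues and add nothing to this one.

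**What to change.** - In Assessment of efficacy and in Statistics, name the 0–48 hour total as the sole primary outcome, as Trial Objectives and Purpose and Trial Design already do.
- List the 0–24 hour total as a secondary outcome wherever secondary outcomes are given. In Statistics, state that it is compared with the same t-test as the primary outcome, because every secondary comparison there now uses a chi-square test.
- Keep 24 hours in Trial Design as a reading time.
- State in both Stopping Criteria and Interim Analysis that a stop for efficacy rests on the 0–48 hour primary outcome only. Changing one section alone would leave the two stopping statements at odds, and barring only the 24-hour total would leave the other secondary outcomes able to end the trial.

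No new data are needed, since both readings are already planned. The cost is that a difference seen only at 24 hours cannot be claimed as primary success. Suppose the whole effect fell on day 1, with a standardised effect of 0.8 there and equal daily SDs (all assumed). The 48-hour effect is then 0.8/sqrt(2 + 2·rho): 0.8/sqrt(2.56) = 0.50 at r = 0.80, 0.8/sqrt(3.24) = 0.44 at r = 0.90 and 0.8/sqrt(3.60) = 0.42 at r = 0.95. Power at 60 per arm would be about 78%, 68% and 63%. The single 48-hour definition already in the Protocol carries this cost today.

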#### Assessment of safety

Following surgery, adequacy of analgesia will be closely monitored, and inadequate analgesia will be treated as per standard protocol in the postanesthetic care unit (PACU). Physical examination of the TAP block injection sites will be performed daily and at the 6 week postoperative follow up visit. Diabetic patients will have blood glucose monitoring as per standard protocol, and all patients will have serial vital signs four times daily. Clinical assessment for severe postoperative nausea and vomiting (PONV) will be performed as per nursing protocol, and by the attending anesthesiologist on daily round. Any serious adverse events will be followed closely until resolution, with frequency of follow up to be determined by clinical judgement. Education to ward nurses will be provided on identification and reporting of adverse events. Adverse events will be recorded in the data collection tool. All serious adverse events will be reported to the Research Ethics Board and Health Canada as per the University of Saskatchewan Serious Adverse Events Reporting Policy and the Health Canada Guidance for Clinical Trial Sponsors document. Any serious unexpected adverse drug events will be reported to Health Canada. During the course of the trial, the sponsor will inform Health Canada of any serious unexpected adverse drug reaction (SUARD) as follows:

- o (a) if it is neither fatal nor life threatening, within 15 days after becoming aware of the information; and
- o (b) if it is fatal or life threatening, within seven days after becoming aware of the information.

Definitions of reactions are as follows:

Serious Adverse Drug Reaction: An adverse drug reaction that requires in-patient hospitalization or prolongation of existing hospitalization, that causes congenital malformation, that results in persistent or significant disability or incapacity, that is life threatening or that results in death.

Serious Unexpected Adverse Drug Reaction (SUADR): A serious adverse drug reaction that is not identified in nature, severity or frequency in the risk information set out in the investigator's brochure or on the label of the drug.

#### **Statistics**

Primary Outcome:

Total opioid consumption at 24 and 48 hours will be gathered from the PCA record and Medication Administration Record (MAR). Intention to treat analysis will be performed. Parametric data will be analyzed with the students t-test for statistical significance.

Secondary Outcome: Opioid consumption in the PACU will be reported in hydromorphone equivalents and compared with chi square test. Length of stay in PACU and length of stay in hospital will be reported as a mean +/- standard deviation (SD), along with confidence intervals and compared with chi square test.

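### The primary comparison is fixed as an unadjusted t-test although useful baseline covariates are obtainable before surgery; the test is valid, but some precision is probably lost

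*Protocol*

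**What the plan says.** The Statistics section of the protocol gives one method for the primary outcome: "Intention to treat analysis will be performed. Parametric data will be analyzed with the students t-test for statistical significance". It mentions no adjusted model. Trial Design describes 1:1 allocation, 60 per arm, from a computer-generated random number table and names no stratification factor.

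The eligible population is broad: "age > 18, ASA class I-III patients scheduled for elective or urgent inpatient laparoscopic/laparoscopic assisted colorectal surgery" (Selection and withdrawal of subjects). Age and ASA class must therefore be known for every patient, and the operation is already scheduled. Trial Design sets the block volume by body weight, "using 1mL/kg of 0.25% bupivacaine with epinephrine 1:200,000", so weight must be known before the block is given. Treatment of subjects sends every participant to a preoperative clinic before the procedure date, and consent follows on the day of surgery. The same section leaves room for more operators: "If there is interest from other general surgeons in participating in the trial, in-person training will be provided to that surgeon".

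The sample size rests on "alpha set at 0.05, power set at 0.08, and the effect size set at 0.8", with a total of 120.

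**The concern.** Opioid use over 48 hours plausibly varies with patient and procedure, and this trial admits a wide mix of both. Neither the randomisation as described nor the named test uses that information. If baseline factors predict consumption, a pre-specified adjusted model estimates the same treatment difference with a smaller standard error. It also corrects for whatever chance imbalance has arisen in those factors.

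At stake is the width of the confidence interval and the power for effects below the planned one. The interval matters because the Trial Objectives present the study as proof of concept to guide later work on dosing and on a comparison with systemic administration. Fixing the covariates in advance also closes off the choice of an adjustment set after the data have been seen.

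An unseen statistical analysis plan does not fully answer this. The protocol does not merely leave the model open; it names the test, and an adjusted primary model elsewhere would depart from it.

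**Working it through.** **Inputs from the protocol.** 120 patients, 60 per arm; alpha 0.05 (sidedness not stated, two-sided assumed); standardised effect 0.8; power printed as 0.08 (0.80 presumably meant). No SD, raw difference or prognostic strength is given.

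**The plan's own figure.** Normal approximation: n per arm = 2(1.960 + 0.842)² / 0.8² = 15.70 / 0.64 = 24.5, so 25. The t-based calculation gives 25.5, so 26 per arm and 52 in total. The stated 120 does not reproduce. That is a separate matter, but it means 0.8 SD does not explain the trial's size.

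**What 60 per arm delivers unadjusted.** Power at 0.8 SD is 99.1% (noncentral t, 118 df). The effect detectable with 80% power is (1.960 + 0.842) × √(2/60) = 0.511 SD by the normal approximation and 0.516 SD by the t-test. The latter is the reference effect below.

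**Effect of adjustment.** Two things act on the variance of the treatment estimate:

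- Explained variance multiplies it by (1 − R²).
- Estimating p covariate parameters multiplies it, on average, by 1 + p/(N − p − 3). Age (1), weight (1), ASA class (2) and planned procedure (1) give p = 5, so the factor is 1 + 5/112 = 117/112 = 1.045.

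The net variance factor is V = (1 − R²) × 1.045. The standard error is multiplied by √V, the equivalent unadjusted sample is 120/V, and power is taken at 0.516/√V with 113 df. R² is an assumption throughout.

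| Assumed R² | SE multiplier | Equivalent patients | Net power at 0.516 SD | Power ignoring the cost of covariates |
|---|---|---|---|---|
| 0 | 1.022 | 115 | 78.2% | 80.0% |
| 0.05 | 0.996 | 121 | 80.3% | 82.0% |
| 0.10 | 0.970 | 128 | 82.3% | 84.0% |
| 0.25 | 0.885 | 153 | 88.6% | 89.9% |

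For example, at R² 0.10, V = 0.90 × 1.045 = 0.940 and 120/0.940 = 128, a gain of about 8 patients. At R² 0.25, V = 0.784 and 120/0.784 = 153, a gain of about 33.

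**Break-even.** V = 1 when R² = 1 − 112/117 = 0.043. Below that, adjustment costs more than it returns.

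**More terms.** With p = 8, for instance after adding surgeon indicators, the factor is 1 + 8/109 = 1.073, and power at R² 0.05 is 79.2%, a small net loss.

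**Other effect sizes, p = 5, R² 0.10–0.25.** At 0.8 SD, power goes from 99.1% to 99.4–99.8%. At 0.4 SD it goes from 58.4% to 61.0–68.9%.

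**The case against.** **Nothing here is an error.** An unadjusted t-test in a 1:1 randomised trial is unbiased and holds its type I error. A reader might infer that chance imbalance, with no stratification, biases the result or undermines the test. It does not: the t-test's standard error already allows for chance imbalance. This part of the objection stands in full, and the point is one of efficiency only.

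**The gain is assumed, and not free.** The protocol gives no prognostic strength for any covariate. A reader might also take the gross figures, 84–90% power or 13–40 extra patients (120 × 0.11 to 120 × 0.33), as costless precision. They ignore the estimation of the covariate terms. The net figures are lower, and there is no gain near R² 0.05. This stands.

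**The planned effect is already covered.** At 0.8 SD the trial has about 99% power, so adjustment adds less than one percentage point there. This stands, and it rules out any inference that the trial is underpowered for its stated target because of the t-test. It does not remove the value of a narrower interval or of power for smaller effects.

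**The data are not all listed.** Weight and planned procedure are implied by dosing and scheduling rather than named as collection items, a colon or rectal split would be a new category, additional surgeons are only a possibility, and the time of randomisation is not stated. The values should be in the chart already used for outcomes, but abstracting them is some work.

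**Covariates are usually left to the analysis plan.** That is fair for the detailed list. It carries less weight where the protocol has already named the primary test, although the sentence is limited to parametric data and does not expressly exclude an adjusted model.

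**Conclusion.** The point holds as a recommended improvement, not as a correction of an invalid analysis. The protocol commits its primary comparison to an unadjusted test while baseline information that may predict the outcome is obtainable before surgery.

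Assuming two-sided alpha 0.05, 60 per arm analysed, about five covariate parameters and R² of 0.10–0.25, the confidence interval narrows by about 3% to 11.5%. If R² is zero it widens by about 2%. The downside is therefore small and bounded, while the upside is moderate and uncertain.

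It ranks below the protocol's more basic statistical problems, notably the printed power ("power set at 0.08") and a sample size that its inputs do not yield.

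**What to change.** Amend the primary-outcome paragraph of the Statistics section to state that the primary analysis is a linear model of the 48-hour opioid total with arm and a short pre-specified list of covariates, for example age, body weight and ASA class. Planned procedure can be added if its categories are defined in advance. Use only values fixed before randomisation. Leave surgeon terms out unless several surgeons take part. Report the unadjusted t-test as a sensitivity analysis.

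Add the chosen covariates to the data collection form, since the protocol does not list them as collected items. Consumption data may be skewed, so the scale on which the total is modelled should be fixed in the same sentence.

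The cost is a sentence or two of protocol text, a few chart items per patient and a few degrees of freedom out of 118. No extra patients or visits are needed.

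### The protocol names a chi-square test for three quantitative secondary outcomes (PACU opioid dose, PACU stay, hospital stay) and defines no categories for any of them

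*Protocol*

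**What the plan says.** The Statistics section of the protocol gives two sentences on the secondary outcomes.

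- PACU opioids: "Opioid consumption in the PACU will be reported in hydromorphone equivalents and compared with chi square test".
- PACU stay and hospital stay: each "will be reported as a mean +/- standard deviation (SD), along with confidence intervals and compared with chi square test".

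For the primary outcome, which is also an opioid amount in hydromorphone equivalents, the same section says: "Parametric data will be analyzed with the students t-test for statistical significance".

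Assessment of efficacy lists the secondary outcomes as PACU stay, "length of stay in hospital, and total opioids administered in the PACU". Trial Design lists the same three, and Trial Objectives and Purpose lists the two stays. None of these sections gives a threshold, cut-point or grouping.

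The Interim Analysis section brings the secondary outcomes into the interim look: "Interim analysis for primary and secondary outcomes, as well as safety parameters, will be performed upon completion of 50% of the total recruitment". It continues: "If statistically significant superiority of either arm is identified, the trial will be terminated".

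**The concern.** A chi-square test compares the frequency of categories between arms and ignores their order and size. It does not compare means, so for the two stays it does not match the mean, SD and confidence interval planned in the same sentence. For PACU opioids it also departs from the t-test that the section gives to the primary outcome, which is the same kind of variable.

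Two things are at stake. First, a test that discards order and size is more likely to miss a real secondary benefit. Second, an analyst following the text would have to invent categories. If that happened after the data were seen, the false-positive rate would no longer be controlled. The interim stopping sentence is not limited to the primary outcome, so read literally these tests could also bear on stopping the trial.

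**Working it through.** The protocol gives no power or error rate for the secondary outcomes, so there is no stated figure to reproduce.

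**Inputs from the protocol.** 60 patients per arm, 1:1 (Trial Design). Alpha 0.05 and "the effect size set at 0.8", with no outcome or unit attached (Selection and withdrawal of subjects). A two-sided test is assumed. A difference of 0.5 SD is added as a more modest effect.

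**1. Chi-square on the recorded values.** Suppose all 120 values differ, as they nearly would for a stay timed finely. Each value forms a row with one patient in one arm and none in the other. The expected count is 0.5 per cell, so each row adds 2 × (0.5² / 0.5) = 1. The statistic is 120 on 119 df, p = 0.457, whether the arms differ by 0 or 5 SD. Read this way, the test says nothing about the difference.

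**2. Chi-square after a median split, normal data assumed.** With a true difference of d SD, the proportions above the common median are Φ(d/2) and Φ(−d/2).

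- t-test power ≈ Φ(d√(n/2) − 1.96). For d = 0.5, n = 60: Φ(0.5 × 5.477 − 1.96) = Φ(0.779) = 0.78.
- Split: p1 = Φ(0.25) = 0.599, p2 = 0.401, difference 0.197. Power ≈ Φ[(0.197 × √60 − 1.96 × √0.5) / √(p1q1 + p2q2)] = Φ[(1.529 − 1.386) / 0.693] = Φ(0.207) = 0.58.
- For d = 0.8 the same formulas give 0.99 and 0.94.
- For 80% power at d = 0.5, the t-test needs 63 per arm and the split needs 100.

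**3. Simulation on skewed, rounded data.** 4,000 runs per scenario, 60 per arm, with values in one arm lower by 0.5 or 0.8 log-SD. The distributions are assumptions, not protocol figures:

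- PACU stay: log-normal, median 90 min, log-SD 0.4.
- Hospital stay: log-normal, median 4 days, log-SD 0.5, rounded up to whole days.
- PACU opioids: log-normal, median 1 mg, log-SD 0.6, in 0.2 mg steps, with and without 15% zero doses in both arms.

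Power (%) at 0.5 / 0.8 log-SD:

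| Outcome | Chi-square, recorded values | Chi-square, median split | Welch t-test |
|---|---|---|---|
| PACU stay, to 1 min | 0.1 / 0.3 | 58.8 / 93.3 | 73.3 / 98.4 |
| PACU stay, to 5 min | 8.0 / 30.8 | 58.9 / 94.1 | 74.6 / 98.8 |
| PACU stay, to 15 min | 24.7 / 71.4 | 57.9 / 92.9 | 73.2 / 98.2 |
| Hospital days | 25.7 / 74.0 | 59.2 / 92.0 | 73.3 / 97.8 |
| PACU opioids, no zeros | 19.6 / 64.2 | 57.8 / 93.5 | 70.0 / 97.5 |
| PACU opioids, 15% zeros | 15.0 / 50.7 | 47.1 / 85.4 | 50.1 / 87.9 |

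Wilcoxon power was 74–75 / 98–99 without zeros and 47 / 85 with them.

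Subtracting columns, the median split loses 12 to 16 points against Welch at 0.5 (from 70.0 − 57.8 = 12.2 to 74.6 − 58.9 = 15.7) and 4 to 6 points at 0.8. With zero doses it loses about 3.

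**4. False positives per outcome, no true effect.** Welch 4.3–5.4%; median split 4.7–5.5%; recorded values 0.0–2.9%. Taking the smallest p over nine cut-points (pooled 10th to 90th percentiles) gives 20.4–24.5%. At the interim (50% of 120 = 60 patients, about 30 per arm; 3,000 runs) that last figure is 18.9–23.5%.

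**The case against.** The strongest reply is that chi-square is a drafting slip. The analyst would run a t-test on the planned mean and SD, and nothing would be lost. That is plausible, but the protocol as it stands prescribes the other test, and an SAP naming a suitable one would contradict it.

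Several limits on the size of the problem are fair:

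- Treating each minute of PACU stay as a category gives a table too sparse for chi-square, and few would do it. The median split is the more realistic comparison. Its loss is modest at 0.8 SD and small for opioids with zero doses.
- The 20 to 25% false-positive rate requires a search over cut-points. The protocol plans no such search, but fixes nothing that would prevent it.
- The assumed hospital stays put some patients at 48 hours or less, although PCA is to run for at least 48 hours. Forcing stays above 48 hours gave Welch 66 / 96% and median split 58 / 93%, so the gap at 0.5 narrows to about 8 points.
- Lost power would make a stop on a secondary outcome less likely. Whether secondary outcomes may stop the trial is a separate defect that changing the test does not cure.

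Trial Design also limits follow-up for secondary outcomes to 48 hours, which conflicts with measuring hospital stay. The same section says this stay can be read from the chart. The conflict needs its own clarification and does not rescue the chi-square test.

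**Conclusion.** The concern holds and should be fixed. For every secondary outcome, the protocol names a test that does not suit the variable, and the text shows this without any calculation. The loss of information is certain; its size depends on an unstated grouping. On the milder reading it is about 20 points of power at 0.5 SD for normal data, 12 to 16 for the assumed skewed data (less with zero doses or a 48-hour floor on hospital stay), and 4 to 6 at 0.8 SD. A median split itself keeps the error rate near 5%; the inflation to roughly 20 to 25% arises only if cut-points are picked after seeing the data. The test named for the primary outcome is not affected.

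**What to change.** In the Statistics section, replace the chi-square test for all three secondary outcomes with one test named before data are seen. Possible wording:

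> PACU opioid dose (hydromorphone equivalents), PACU stay and hospital stay will each be summarised by mean and SD per arm and compared with a two-sample Welch t-test, with the 95% confidence interval for the difference in means.

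This matches the summary already planned for the two stays and adds a mean and SD for PACU opioids. On the skewed data simulated here, its power was within about 5 points of the Wilcoxon test. If a rank method is preferred because doses and stays are likely to be skewed, name the Wilcoxon rank-sum test with a Hodges-Lehmann difference and its 95% confidence interval. If categories are really wanted, state the cut-points in the protocol before data are seen and accept the loss of power.

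The cost is wording only. The doses and stays are already to be taken from the chart and the medication record, and no patients or visits are added. The 48-hour follow-up statement should be reconciled with hospital stay at the same time.
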